• NIH-TB List Sorting Working Memory Test					
• NIH-TB Pattern Comparison Test					
Lifestyle Counseling	x	x			
Registered Dietician Visit	x	x			
Drug Dispensing	x		x		
Adherence	← Assessed at in person visits via electronic prescription bottles and pill count and at weeks 2 and 4 via phone call →				
Side Effects, Inter-current Illnesses, Concomitant Medications Review	← Assessed weeks 6, 8, 10, and 14 at study visit; weeks 2, and 4 via phone call →				

¹ Will be reviewed by study principal investigator and/or co-investigator

² Demographics including age, sex, race/ethnicity

³ Physical exam does not need to be repeated if one was done by CPOM faculty, in the pediatric weight management clinic, or by a pediatric endocrinologist within 30 days prior to Screening/Baseline visit. Tanner determined by Marshall-Tanner criteria examining breast and pubic hair development (girls) or genitalia and pubic hair (boys); to be performed by a trained professional.

⁴ Height, weight, BMI, waist circumference, hip circumference

⁵ Creatinine (to assess renal function) and bicarbonate (to assess for presence of metabolic acidosis)

⁶ Lipids (total, LDL-, HDL-cholesterol, triglycerides), glucose, insulin, hemoglobin A1c.

⁷ DNA collection via salivary collection kits

⁸ iDXA to include total and regional body fat measures

⁹ Performed using Tanita scale

¹⁰ Including hunger/satiety Visual Analog Scales, Adult Eating Behavior Questionnaire (AEBQ), Food Craving Questionnaire-Trait-Reduced (FCQ-T-r), Dimensional Yale Food Addiction Scale 2.0 for Children (dYFAS), Reward Based Eating Drive Scale X5 (RED-5), and Physical Activity Questionnaire for Adolescents (PAQ-A)

¹¹ Assessed via the Beverage Intake Questionnaire 15 (BEVQ-15)

¹² PHQ-9 to be conducted at Baseline/Screening, Week 6 and Week 10. Columbia-Suicide Severity Rating Scale (C-SSRS) to be conducted at all visits

¹³ Controlled Oral Word Association (COWA) test, NIH-TB List Sorting Working Memory Test and NIH-TB Pattern Comparison Test

¹⁴ Urine pregnancy preferred, but serum may be utilized. Females who undergo pregnancy testing will be asked to complete a questionnaire about their experience at the Week 14 visit

MEDICAL PROTOCOL (HRP-590)

PROTOCOL TITLE: Pharmacokinetics and Pharmacodynamics of Topiramate for Weight Loss in Youth: PHARMATOP

VERSION DATE: 05/03/2024

5.2 Study Procedures:

Anthropometric Measurements and Body Fat Composition:

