Blood pressure measurements will be obtained manually on the same arm using the same cuff size and equipment. Standardized procedures will be employed as described previously.³⁷ Individual cuff size will be determined by measuring the arm circumference midway between the acromial process and the bony olecranon. Sitting blood pressure and heart rate will be measured after the participant has been resting quietly for 10 minutes. Measurements will be made three consecutive times (3-minute intervals). The final two of three measurements will be averaged.

Cardiometabolic risk factor labs will be drawn fasting (≥ 12 hours) and will include measurements of plasma glucose (FPG), plasma insulin (FPI), hemoglobin A1C, and lipids (total-, LDL-, HDL-cholesterol, and triglycerides). These will all be assayed in Fairview Diagnostics Laboratories (Minneapolis, MN – a Center for Disease Control and Prevention certified laboratory). The fasting insulin and glucose measures will be used to determine a HOMA-IR, a commonly used surrogate

Figure 3: Tanita® Scale

MEDICAL PROTOCOL (HRP-590)

PROTOCOL TITLE: Pharmacokinetics and Pharmacodynamics of Topiramate for Weight Loss in Youth: PHARMATOP

VERSION DATE: 05/03/2024

marker of insulin resistance in children and adults,³⁸ which will be calculated per standard convention:

$$\text{FPG (nmol/l)} \times \text{FPI (microU/l)} / 22.5$$

Topiramate levels will be drawn at 6, 8, 10, and 14 weeks, corresponding to 4, 6, 8, and 12 weeks after the participant has reached 75 mg daily (or the maximum tolerated dose). All topiramate samples will be spun at 10,000 x g for 10 minutes, 5 to <120 minutes after blood draw, and frozen (-80°C) until analysis per standard protocol.³⁹ We will measure topiramate concentrations by a previously validated liquid chromatography-mass spectrometry (LCMS) assay in the lab of [name] (Department of Experimental and Clinical Pharmacology, College of Pharmacy, University of Minnesota).³⁹

DNA Collection and Genotyping:

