	Adult Eating Behavior Questionnaire (AEBQ)	Hunger, satiety, emotional eating, hedonic eating	35	1, 2, 5
	Food Craving Questionnaire-Trait – Reduced (FCQ-T-r)	Food craving	15	1, 2, 5
	Dimensional Yale Food Addiction Scale 2.0 for Children (dYFAS)	Food addiction	13	1, 2, 5
	Reward Eating Drive Scale X5 (RED-5)	Binge eating features	5	1, 2, 5
	Beverage Questionnaire (BEVQ15)	Sugar beverage intake	15	1, 2, 5
Physical Activity	Physical Activity Questionnaire for Adolescents (PAQ-A)	Physical activity	9	1, 2, 5
Neurocognitive Testing	Controlled Oral Word Association	Verbal fluency	3	1, 2, 4, 5
	NIH-TB List Sorting Working Memory Test	Working memory	N/A (up to 7 minutes to complete)	1, 2, 4, 5
	NIH-TB Pattern-Comparison Processing Test	Processing Speed	N/A (up to 1.5 minutes to complete)	1, 2, 4, 5
Safety Questionnaires	Eating Disorder Examination Questionnaire (EDE-Q)	Eating disorders	28	1, 2, 5
	Patient Health Questionnaire-9 (PHQ-9)	Depression	9	1, 2, 4
	Columbia-Suicide Severity Rating Scale (C-SSRS)	Risk for Suicidality	Up to 10	1, 2, 3, 4, 5

Safety-Related Assessments:

Please see **Table 1**. A creatinine and bicarbonate to assess for renal disease and metabolic acidosis will be performed at baseline and one month after topiramate has reached the maximum dose in this study (75 mg or maximum-tolerated dose). We will require all female participants to confirm use of two forms of contraception if sexually active.

We will monitor for depression, suicidal behavior and ideation, acute secondary angle closure glaucoma, renal stones, cognitive impairment, decreased bicarbonate indicating metabolic acidosis, and elevated creatinine. Changes in neurocognitive function (verbal fluency) and working memory will be evaluated using the Controlled Oral Word Association (COWA) test and the NIH-TB List Sorting Working Memory Test, and NIH TB Pattern Comparison Processing Test, respectively, at each in-person study visit, aside from the week 8 blood draw-only visit.⁴⁹⁻⁵⁰ Of note, the COWA is sensitive for phonetic fluency and has been used in multiple studies involving topiramate.⁵¹⁻⁵³

Participants will be assessed for depression with the Patient Health Questionnaire-9 (PHQ-9) at the Screening/Baseline, Week 6 and Week 10 visits. Participants will be assessed for suicide with

MEDICAL PROTOCOL (HRP-590)

PROTOCOL TITLE: Pharmacokinetics and Pharmacodynamics of Topiramate for Weight Loss in Youth: PHARMATOP

VERSION DATE: 05/03/2024

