the Columbia-Suicide Severity Rating Scale (C-SSRS) at all visits.⁵⁴⁻⁵⁵ A participant will be referred to a mental health provider (MHP) or primary care provider if the participant has a PHQ-9 score of ≥ 15 , any suicidal behavior, or any suicidal ideation of type 4 or 5 on the C-SSRS and a member of the study team may contact a participant's existing mental health provider if a participant presents with acute suicidal ideation/behavior at a study visit. The decision as to whether the participant will be allowed to continue in the trial will be made by the local medical monitor ([name]) in consultation with the MHP or primary care provider after the referral clinical visit. Participants who already have an existing mental health provider and/or are followed by their primary care provider for mental health will have their mental health provider and/or primary care provider alerted if the participant has a PHQ-9 score of ≥ 15 or any suicidal behavior or suicidal ideation of type 4 or 5 on the C-SSRS.

Eating disorders will be evaluated using the eating disorder examination-questionnaire (EDE-Q).⁴⁶ Any participant endorsing vomiting, laxative use, and/or diuretic use for weight control (via the EDE-Q by standard scoring procedures), will be interviewed by a pediatric behavioral psychologist using the Eating Disorders Module of the Structured Clinical Interview for Diagnostic and Statistical Manual of Mental Disorders, 5th Edition (DSM-5). If disordered eating is present upon clinical interview, the participant will be removed from the study and referred to an eating behavior specialist for clinical follow-up. If no eating disorder is present, the participant may continue in the study.

5.3 Study Duration:

14 weeks, including 2 weeks of topiramate titration up to 75 mg daily (or maximum tolerated dose; as described in **Section 4.1**) followed by 12 weeks on topiramate.

5.4 Use of radiation:

The iDXA consists of exposure to 0.01 mSv. In comparison, a resident of the State of Minnesota receives approximately 3 mSv from natural background radiation as a result of living in Minnesota. There are no other sources of radiation in this study.

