PROTOCOL TITLE: Pharmacokinetics and Pharmacodynamics of Topiramate for Weight Loss in Youth: PHARMATOP

VERSION DATE: 05/03/2024

- Depression and suicide screening (PHQ-9 and C-SSRS). Participants whose tests show that they have active suicidal ideation will be referred to their own mental health provider, have a mental health referral generated or be referred to the emergency department
- Neurocognitive testing (COWA test, NIH-TB List Sorting Working Memory Test, NIH-TB Pattern Comparison Processing Speed Test)
- Lifestyle and registered dietitian counseling

Week 2 (± 7 days from enrollment):

- Side effects, inter-current illnesses, medication review and adherence (via phone call)

Week 4 (± 7 days from enrollment):

- Side effects, inter-current illnesses, medication review and adherence (via phone call)

Week 6 (± 7 days from enrollment; Visit 2):

- BMI/Anthropometrics
- Blood pressure and heart rate
- Blood draw for safety labs (creatinine and bicarbonate)
- Pregnancy test for females
- Topiramate concentration
- Bioelectrical impedance analysis (via Tanita Scale)
- Eating behavior and physical activity questionnaires (hunger/satiety visual analog scales, AEBQ, FCQ-T-r, dYFAS, RED-5, BEVQ-15, PAQ-A)
- Safety questionnaire for eating disorders (EDE-Q)
- Depression and suicide screening (PHQ-9 and C-SSRS)
- Neurocognitive testing (COWA test, NIH-TB List Sorting Working Memory Test and NIH-TB Pattern Comparison Processing Speed Test)
- Lifestyle and registered dietitian counseling
- Side effects, inter-current illnesses, medication review
- Adherence (via electronic prescription bottle review and counting pills)

Week 8 (± 7 days from enrollment; Visit 3; lab draw only):

- Topiramate concentration
- Side effects, inter-current illnesses, medication review (via phone call or in-person)
- Adherence (via electronic prescription bottle review and counting pills)
- Suicide screening (C-SSRS)
- Drug dispensing

Week 10 (± 7 days from enrollment; Visit 4):

- BMI/Anthropometrics
- Blood pressure and heart rate

MEDICAL PROTOCOL (HRP-590)

PROTOCOL TITLE: Pharmacokinetics and Pharmacodynamics of Topiramate for Weight Loss in Youth: PHARMATOP

VERSION DATE: 05/03/2024

- Pregnancy test for females
- Topiramate concentration
- Bioelectrical impedance analysis (via Tanita Scale)
- Depression and suicide screening (PHQ-9 and C-SSRS)
- Neurocognitive testing (COWA test, NIH-TB List Sorting Working Memory Test, NIH-TB Pattern Comparison Processing Speed Test)

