- Side effects, inter-current illnesses, medication review
- Adherence (via electronic prescription bottle review and counting pills)

Week 14 (± 7 days from enrollment; Visit 5):

- Physical exam, performed by a trained pediatrician
- BMI/Anthropometrics
- Blood pressure and heart rate
- Blood draw for cardiometabolic risk labs (lipids, glucose, insulin, and A1c)
- Pregnancy test for females and questionnaire about the testing
- Topiramate concentration
- Bioelectrical impedance analysis (via Tanita Scale)
- Safety questionnaire for eating disorders (EDE-Q)
- Eating behavior and physical activity questionnaires (hunger/satiety visual analog scales, AEBQ, FCQ-T-r, dYFAS, RED-5, BEVQ-15, PAQ-A)
- Neurocognitive testing (COWA test, NIH-TB List Sorting Working Memory Test, NIH-TB Pattern Comparison Processing Test)
- Side effects, inter-current illnesses, medication review
- Suicide screening (C-SSRS)
- Adherence (via electronic prescription bottle review and counting pills)

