A charter for the DSMB will be developed and approved by its members along with a plan for frequency of data review prior to the commencement of the study. Review materials for the DSMB will be prepared and presented by the study biostatistician, [name]. A report from each meeting will be sent to the PI and co-investigators advising on the continuation of the study and any suggestions for trial improvement. This report will also be sent to the assigned NIH Program Director and the IRB. Important charges of the DSMB will be to closely monitor progress and timelines related to recruitment goals, fidelity to the protocol (e.g. regularly review the number and types of protocol deviations), and to closely monitor the quality and integrity of the data. The DSMB will communicate any concerns relevant to these issues of study conduct to the PI and note specific recommendations for improvement in meeting reports.

In the event that a participant has a serious adverse event that is deemed related to topiramate (this is an open-label study; all participants will receive topiramate) and/or procedures by either the internal or external medical monitor, the participant will be required to discontinue the intervention following the withdrawal procedures as outlined in **Section 12.2**. The overall study may be stopped at any time at the request of the PI, internal or external medical monitor and/or the DSMB. Participants may be removed from the study if suicidal ideation is present at any time during the trial or if any clinically significant changes (at the discretion of the internal or external medical monitor) in mood and/or depression are observed (see **Section 5.2**). Patients will be instructed that they may withdraw from the study at any time and for any reason.

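### Structured monitoring of the risks named in section 5.2 does not span the 14 weeks of treatment: bicarbonate and creatinine end at week 6, PHQ-9 ends at week 10, and no mood or suicidality instrument falls between baseline and week 6

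*Combined protocol and SAP*

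**What the plan says.** Section 5.2 (Safety-Related Assessments) lists the risks to be monitored, among them depression, suicidal behavior and ideation, decreased bicarbonate and elevated creatinine. The measurements behind that list are as follows.

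- **Safety labs.** Creatinine and bicarbonate "will be performed at baseline and one month after topiramate has reached the maximum dose in this study". Section 8.3 lists "Blood draw for safety labs (creatinine and bicarbonate") at week 6. It does not list these analytes at weeks 8, 10 or 14, although blood is taken at each of those visits for the topiramate level. The other week 14 laboratory entry is "Blood draw for cardiometabolic risk labs (lipids, glucose, insulin, and A1c").
- **PHQ-9.** Footnote 12 of Table 1 reads "PHQ-9 to be conducted at Baseline/Screening, Week 6 and Week 10". Table 2 (visits 1, 2 and 4), the text of section 5.2 and section 8.3 agree with it.
- **C-SSRS.** Given at all five visits: baseline and weeks 6, 8, 10 and 14.
- **Weeks 2 and 4.** Section 8.3 lists only "Side effects, inter-current illnesses, medication review and adherence (via phone call"). No PHQ-9 or C-SSRS is listed.

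Section 18.2 provides that "Participants may be removed from the study if suicidal ideation is present at any time during the trial". It also allows removal for clinically significant changes in mood or depression, at a medical monitor's discretion, and refers to section 5.2. Section 5.3 gives the treatment period as "14 weeks, including 2 weeks of topiramate titration up to 75 mg daily", followed by 12 weeks on drug.

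**The concern.** The stated aim is wider than the collection that supports it. A fall in bicarbonate or a rise in creatinine without symptoms cannot be found by asking about side effects, and after week 6 nothing else is scheduled that would show it. Depression at exit is not scored, while cognition, the EDE-Q, pregnancy testing and the C-SSRS are all repeated at week 14. During titration and the first four weeks at full dose, detection of mood change or ideation depends on a general phone inquiry.

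Two features of the plan make the missing exit values matter more. Section 12.3 expects that many completers may continue topiramate, so week 14 is a handover point. Section 12.2 stops data collection when a participant chooses to withdraw, so someone who does so before week 6 contributes no scheduled on-drug bicarbonate, creatinine, PHQ-9 or C-SSRS. Section 15.2 allows for 25% drop-out but does not say when it is expected.

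**Working it through.** This is schedule arithmetic; no power or alpha figure bears on it.

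**Inputs.** Treatment lasts 14 weeks (section 5.3), or 14 × 7 = 98 days. Full dose is reached at week 2 (sections 4.1 and 5.3). Visits fall at weeks 6, 8, 10 and 14, each ±7 days (section 8.3). Drug is assumed to start at the baseline visit, where Table 1 places the first dispensing.

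**Reproducing the plan's own timing.** Week 2 + 4 weeks = week 6. Section 5.2 places the topiramate levels at weeks 6, 8, 10 and 14, "corresponding to 4, 6, 8, and 12 weeks after the participant has reached 75 mg daily" or the maximum tolerated dose. The one-month lab and the week 6 visit therefore coincide, and the text, Table 1 and section 8.3 agree.

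**Gaps at nominal visit days** (week 6 = day 42, week 10 = day 70, week 14 = day 98):

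| Measurement | Scheduled weeks | Interval without it | Days | Share of 98 days |
|---|---|---|---|---|
| Bicarbonate, creatinine | 0, 6 | week 6 to 14 | 98 − 42 = 56 | 57% |
| PHQ-9 | 0, 6, 10 | week 10 to 14 | 98 − 70 = 28 | 29% |
| PHQ-9 and C-SSRS, first on-drug | 6 | baseline to week 6 | 42 | 43% |

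The later C-SSRS gaps are 2, 2 and 4 weeks, with none left at week 14. Of the 12 weeks at full dose, 8 (67%) have no scheduled bicarbonate or creatinine.

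**With the ±7-day windows.**
- Labs: from 91 − 49 = 42 days to 105 − 35 = 70 days.
- PHQ-9: from 91 − 77 = 14 days to 105 − 63 = 42 days.
- First on-drug screen: from 35 to 49 days after baseline (36% to 50% of 98).

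**Which rules depend on what.** The section 5.2 referral triggers are PHQ-9 of 15 or more, any suicidal behavior, or C-SSRS ideation of type 4 or 5. At week 14 the C-SSRS triggers can operate and the PHQ-9 trigger cannot. The removal provision in section 18.2 names no instrument.

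**Effect of adding week 14 values.** Each of these measures would then have a value at the end of treatment. The week 6 to week 14 lab interval would still be 56 days, and PHQ-9 would still have a 28-day interval before its last value.

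**The case against.** The best defence is that section 5.2 defines its own scope. The lab schedule stands just before the list of monitored risks and the PHQ-9 and C-SSRS schedule just after it, and neither promises collection to week 14. Section 13.7 has staff ask about adverse events at every encounter, and section 13.1 lists suicidal behavior and ideation as a topiramate reaction with a referral path. The week 6 C-SSRS may look back over the early weeks, though its version and recall period are not stated. Section 12.3 arranges clinic follow-up for those who stay on drug. Section 4.1 describes the target dose as well tolerated in the group's earlier trial, safety is not a stated objective, and the documents give no time course for any of these risks.

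Most of this stands, and it rules out several stronger readings that a reader might infer:

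- *Table 1 contradicts its own footnote at week 14.* It does not. The row combines depression and suicide screening, and footnote 12 gives the C-SSRS at all visits, which accounts for the marks at weeks 8 and 14.
- *A full chemistry is already drawn at week 14.* The panel is lipids, glucose, insulin and A1c only.
- *Nothing screens for suicidality before week 6.* No structured instrument does, but staff do ask about side effects and adverse events.
- *The removal rule cannot operate.* It is permissive and needs no particular instrument.
- *On-treatment safety cannot be described.* Adverse events, C-SSRS, cognition and EDE-Q all run to week 14.

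The defence does not supply a reason for ending the labs at week 6 or PHQ-9 at week 10, nor a way to detect a silent laboratory change after week 6.

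**Conclusion.** The concern holds as a gap between stated monitoring and scheduled measurement. Bicarbonate and creatinine have no scheduled value for the last 56 of 98 days (57%; 42 to 70 days with windows). PHQ-9 has none for the last 28 days (14 to 42 with windows), which removes one referral trigger at exit. No PHQ-9 or C-SSRS is scheduled for the first 42 days on drug (43%; 35 to 49 days with windows).

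These figures assume that treatment starts at baseline and that titration takes the planned two weeks. They measure how long structured collection is absent. They do not measure how many events would be missed, and the documents give no basis for that estimate. The point does not affect the primary pharmacokinetic or pharmacodynamic analyses. It merits a short amendment because the participants are adolescents and the remedy for the exit values is cheap.

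**What to change.** Reconcile sections 5.2 and 18.2 with Table 1 and footnote 12, Table 2 and section 8.3, so that what is collected matches the monitoring stated, or state and justify the narrower scope.

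For the exit visit, the low-cost data-collection step is to run creatinine and bicarbonate on the existing week 14 blood draw and to collect PHQ-9 at that visit. Footnote 12, Table 2 and the affected text of sections 5.2 and 8.3 would change together. This supplies end-of-treatment values; it does not shorten the week 6 to week 14 lab interval. The change log shows that version 16 made additions of the same kind.

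For baseline to week 6, the sponsor and medical monitors should decide, and write down, whether the inquiry at the week 2 and 4 calls is enough to support the any-time wording in section 18.2. A phone-administered instrument would not be a free addition, because a positive remote screen in a minor needs a handling pathway. That choice, like the referral thresholds, dosing and stopping rules, is left to the sponsor.

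The cost is two more analytes, nine more questionnaire items, a few more results to review and a short amendment.

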5.5 Use of Center for Magnetic Resonance Research: N/A

6.0 Data and Specimen Banking

6.1 Storage and Access:

Blood Samples:

Blood samples for lipids (total-, HDL-, and LDL-cholesterol and triglycerides), glucose, insulin, and hemoglobin A1c will be sent to the Fairview Diagnostics Laboratory (which is CLIA licensed) after collection of the sample.

DNA Specimens:

The DNA specimens (saliva kits) will be stored in the Pediatric Research BioBank until processing, located in the [name]. These specimens will then be transferred to the University of Minnesota Genomics Center for DNA extraction, quantification, and genotyping. After completion of these steps, specimens will then be transferred back to the Pediatric Research BioBank, where they will be banked for future use. We will bank these samples indefinitely. DNA

MEDICAL PROTOCOL (HRP-590)

PROTOCOL TITLE: Pharmacokinetics and Pharmacodynamics of Topiramate for Weight Loss in Youth: PHARMATOP

VERSION DATE: 05/03/2024

specimens will only be handled by the study personnel including the study investigator, co-investigators, and coordinator(s).

Electronic Health Record (EHR) Data Storage and Access:

Identifiable information from the EHR will only be accessed through the AHC-IE, which is a secured data shelter, and only via UMN-issued encrypted password-protected computers. Only study investigators will have access to the data, and sharing of the data will only be via the ACE-IE secured data shelter, UMN Box, and REDCap. We will work with UMN Best Practices Integrated Informatics Core (BPIC) for EHR data gathering, storage, and preparation for analysis.

6.2 Data:

Results from the Fairview Diagnostics Laboratories will be posted to the patient's chart and will also be logged into REDCap. The data will be kept with a unique identification (ID) link. The principal investigator will retain the link to the patients' names, which will be stored in the ACE-IE and only accessed via UMN-issued encrypted password-protected computers. Data, including results from Fairview Diagnostics Laboratories, will be entered into a REDCap database on the secure web interface with data checks used during data entry to ensure data quality. REDCap is a widely-used, powerful, reliable, and well-supported system. REDCap includes a complete suite of features to support HIPAA compliance, including a full audit trail, user-based privileges, and integration with the institutional Lightweight Directory Access Protocol (LDAP) server. The database and web server are both housed on secure servers operated by UMN Health Sciences Technology (HST). The servers are in a physically secure location on the UMN campus and are backed up nightly, with the backups stored in accordance with the HST retention schedule of daily, weekly, and monthly tapes retained for 1 month, 3 months, and 6 months, respectively. The HST servers provide a stable, secure, well-maintained, and high capacity data storage environment. Access to the study's data in REDCap will be restricted to members of the study team by username and password.

6.3 Release/Sharing:

Access to the study data REDCap will be restricted to the members of the study team by username and password.

